4.3 Study Enrollment Procedures

Recruitment Methods

Randomized Control Trial: When a patient arrives in the participating ED (UH Cleveland Medical Center ED (site 1), the Vanderbilt University Medical Center (VUMC) ED (site 2) and the Hillcrest University of California San Diego (UCSD) ED (site 3)), they will be triaged by the triage nurse per current ED procedures. Pending permission of site ED leadership, pre-treatment study flyers can be posted at triage, in waiting areas, or in treatment spaces to offer a passive introduction to the study. Within the triage unit, potential subjects will be identified flagged by nursing staff and/or a member of the research staff. Patients who rate pain four or greater on the 11-point NRS scale will be considered for the study. At that time, the Study Coordinator (SC) or the Research Assistant (RA) will verify the patient's initial eligibility (age, understanding of English language, presence of pain) using the EHR. If the patient is potentially eligible, the SC or RA, if able, will approach the patient while in the waiting room to be seen by their provider to hand them the patient recruitment flyer. The SC or RA will continue to monitor his or her status and location within the ED using the EHR. The patient will then be roomed and seen by the ED clinical provider. If the ED provider determines that patient does not have a clinical condition prohibiting study participation, s/he will sign a study approval form and give back to the SC or RA. Thereafter, the SC or RA will approach the potential subject to introduce the study. If the person is interested in study participation after they have been assigned to a room, the SC or RA will assess patient's capacity to understand and sign documentation, if patient is capable then they will seek to obtain informed consent. The consent will inform the patient that if they are randomized to receive acupuncture a study team member may contact them to ask if they would like to participate in an additional interview, and that they may refuse to participate in the interview portion of the study without affecting their participation in the other portion of the research. They will be informed that the interview will be recorded and transcribed and that a study information sheet will be shared and reviewed with them prior to the start of the interview. If the patient is not interested in participating in the study or refuses to provide their phone number and email for follow up assessments, a reason for refusal will be documented by the SC or RA in our computerized study database.

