6.2 Description of Evaluations

6.2.1 Screening Evaluation

At each ED, the Study Coordinator (SC) or Research Assistant (SC) and acupuncturist will work as a team, staffing an average 2.5, 4-6 hour recruitment/intervention sessions per week, varying the times

and days across sites as this may influence adoption. As in Figure 1, after the ED RN conducts the initial triage activity, the SC or RA (“study staff”) will identify and conduct initial eligibility pre-screening in the in the ED triage unit. The patient will then be roomed and seen by the ED clinical provider. If the ED provider determines that patient does not have a clinical condition prohibiting study participation, s/he will sign a study approval form (see below). The study staff will then approach the patient for study participation.

Provider sign off

Acupuncture in the Emergency Department for Pain Management (ACUITY)

If the patient is randomized to the acupuncture arm, please withhold pain and anxiety medications until after the acupuncture session.

The study coordinator will inform you what arm they are assigned to and when their session has ended.

In order for this patient to be eligible to participate in the "Acupuncture in the ED" study, please verify you have examined the patient and believe to the best of your knowledge, at this time, that the patient does not have the following conditions:

Critical status / Trauma
 Bone fracture
 Joint dislocation
 Migraine
 Psychological / psychiatric concern
 Clinical judgement / Other:

If you deem the patient eligible for the study, the patient will be randomized to acupuncture or usual care.

Patient can continue in study
 Patient is excluded from study

Sign: _____

Consenting Procedure

We have requested a partial HIPAA waiver for prescreening. Therefore, patients will only be consented once the screening process is over and eligibility is confirmed.

The consent process will occur after the patient has gone through the triage process and been assigned to a room within the ED. The consent process will be conducted by dedicated research staff (SC or RA) that have been trained in obtaining informed consent and who have current Human Subjects Protection and Good Clinical Practice certifications. The status and location of the patient will be monitored by

research staff using the EHR to ensure the patient is approached at an appropriate time.

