9.5 Outcomes

Implementation and Treatment Outcomes

All data analyses will be preceded by extensive data checking and verification to identify and resolve the reasons for missing values, inconsistencies, and out-of-range values. Although we anticipate little missing data based on our experience, we will carefully examine whether missingness is completely at random, at random or informative. Models proposed for analysis can handle incomplete data but do

require at least that missingness be at random. Descriptive statistics of primary outcomes: pain intensity change scores for Pre-Treatment to Post-Treatment and Pre-treatment to ED Discharge as well as secondary outcomes will be conducted to assess their distribution overall and by sites as well as demographic characteristics (e.g. sex, age group, race, household income, pain location among others). The variables will be summarized using descriptive statistics (sample size, mean, standard deviation, median, minimum, and maximum) for continuous variables and by the number and percentage of patients for categorical variables. We will report 95% exact confidence interval of median⁸³ for the key continuous variables and 95% exact binomial confidence interval⁸⁴ for categorical variables. All assessments will include sex as a biological variable as described below.

Feasibility of Recruitment and Retention

We will assess recruitment rates (# enrolled / # eligible), pace of accrual, data completeness, and retention at each data collection point, overall and across sites. We will assess variables across different patient groups (including age, race, sex), and across the study arms. Provider adoption will be assessed by the proportion of their eligible patients that clinicians approve for study participation. We will assess variables across different provider characteristics (including age, race, sex), and across the study sites. Completeness of data collection and retention at each time point: we will also track completeness of data collection, and patterns and proportions of missing data at each time point. We will compare these proportions overall and across sites and by demographics as described above.

Acceptability

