Overall approach. We base our selection of implementation outcomes on the synthesis and recommendations outlined by Proctor et al in their authoritative 2011 paper.⁸⁶ We include all of the early phase outcomes, excluding cost, proposed in this widely cited framework, including: Feasibility (“practicability”), provider adoption, perceptions of appropriateness, acceptability, and treatment fidelity. These will be assessed both quantitatively and qualitatively. In addition to implementation outcomes, we will also examine implementation processes, strategies, stakeholder experiences, and barriers and facilitators to implementation using both qualitative interviews and real-time observations. For a list of implementation constructs, variables, and data sources, see Table 1.

Table 1: Implementation Variables and Sources

Construct	Variable	Data Collection/Source
Outcomes		
Feasibility		
• Recruitment • Uptake	# recruited patients / # eligible # completed sessions /# recruited	Study records Provider assessment, real-time observations, qualitative interviews
Adoption	# approved / # recruited	Study records
Appropriateness	Suitability for ED setting	1 item survey, qualitative interviews
Acceptability	Satisfaction/helpfulness	1 item survey, qualitative interviews
Fidelity	Adherence to Responsive Manualization	[name] reviews study records and discusses with study acupuncturists
Stakeholder strategies	Processes and steps taken	Qualitative Interviews
Barriers and facilitators	Strengths/weaknesses of the program Contextual influences at patient, provider, local, and institutional level	Qualitative interviews/structured observation

Aim 2b1. Assess Implementation outcomes: feasibility, adoption, appropriateness, and acceptability.

Feasibility is defined as the degree to which AC can be successfully implemented in the ED setting. This is operationalized as **recruitment** (see Aim 2a); and **uptake** (the proportion of recruited patients who receive a complete AC session, measured by a single question assessment: “*Did patient xx receive a completed treatment session at this visit?*”). Feasibility of the study will also be assessed qualitatively, through stakeholder interviews focusing on barriers and facilitators to implementation, and real-time observations of the uptake of the intervention in the ED setting. For a description of qualitative data collection and analysis, see section 2b2 below.

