Provider adoption is defined as the intention to engage with the innovation/intervention. This is operationalized as the proportion of an ED physician’s recruited patients who are approved for study participation. As elsewhere, we will assess variables across different provider characteristics (including age, race, sex), overall and across the study sites to assess group differences in this outcome and those below.

Perception of appropriateness is defined as the perceived **suitability** of the intervention to the ED setting. ED providers will be asked: “*To what degree do you view the acupuncture intervention as useful or suitable for this ED setting?*” (1-very appropriate—5-Very inappropriate); Perceptions of appropriateness will also be explored through qualitative interviews.

‘Acceptability’ is defined as perceptions of the palatability of an innovation, or satisfaction by stakeholders with aspects of an innovation. It is more specific than overall satisfaction with a service.⁹⁹ For this study, acceptability among ED staff is operationalized in our quantitative assessment as satisfaction with the acupuncture intervention as delivered in the ED setting. **Providers** will answer two questions regarding their general opinion about acupuncture: “Do you view acupuncture in general as an appropriate intervention for the ED setting?” Likert scale (1-very appropriate—5-Very inappropriate) and “Do you view acupuncture in general as helpful in managing patient pain in the ED?” Likert scale (1-Very helpful—5- Not at all helpful). And two questions regarding the delivery of ACUITY study in the ED: “Were you satisfied with how the ACUITY acupuncture intervention was delivered in your setting?” Likert scale (1-Very satisfied—5-Very dissatisfied) and “Did the ACUITY project impose a burden on ED staff in your setting?” Not a burden, Somewhat of a burden, Moderate burden, Extreme burden.

Acceptability of the intervention will also be explored in depth in semi structured stakeholder interviews.

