3. UCSD

SECTION 1 – Patient Identifiers. Automatically generate sequential numbers when adding a new patient. Verify MRN has not previously been randomized; if MRN has, auto populate exclusion with “yes”.

1. Name: [FREE TEXT]
2. MRN: Numerical character limit of 8
3. Date of ED visit / screening

SECTION 2 – Inclusion / Exclusion Criteria To be completed by research coordinator per EHR / patient report.

Yes	No	
		Inclusion Criteria – ALL must be “Yes”
x		1. ≥ 18 years of age
x		2. Ability to communicate in English
x		3. Level 3, 4, 5 on triage rate scale
x		4. Acute musculoskeletal, back, pelvic, non-cardiac chest, abdominal, and headache pain (≥ 4 on the NRS) due to non-penetrating injury.
		Exclusion Criteria – ALL Must be “No”
x		5. Fever exceeding 100° F
x		6. Presenting with a chief complaint of a psychological / psychiatric concern
x		7. Presenting with chief complaint of Migraine
x		8. Current Pregnancy
x		9. Self-reported or documented opioid medication taken orally within 4 hours
x		10. Presenting with chief complaint of Joint Dislocation
x		11. Presenting with chief complaint of Bone Fracture
x		12. Confirmed or suspected COVID-19

1. Participant’s status based on the screening?
 - a. Eligible
 - b. Non eligible
 - c. Unable to ascertain

SECTION 3 – Provider Verification To be completed by research coordinator

1. Is the Provider Sign Off form completed and signed?

- a. Yes
- b. No **(END PROCESS)**

- c. Did not receive from Provider **(END PROCESS)**
 - i. If yes, what is the patient's status per the ED provider?
 - 1. Eligible
 - 2. Not eligible
 - a. If not eligible, what reason was indicated? **(END PROCESS)** [FREE TEXT]

SECTION 4 – Consent To be completed by research coordinator.

- 1. Did the patient consent to participate?
 - a. Yes
 - i. If yes, which follow up method did they choose?
 - 1. Phone/text: 10 digit verification
 - 2. Email: [FREE TEXT]
 - 3. Both: 10 digit verification and free text (IDEAL)
 - b. No
 - i. Reason for refusal? **(END PROCESS)**
 - 1. Not interested in study
 - 2. Study will take too much time
 - 3. Family present
 - 4. Acupuncture or needle fear
 - 5. OTHER [FREE TEXT]
- 2. Did the patient share their mailing address for remuneration?
 - a. Yes
 - i. If yes, please enter: [FREE TEXT]
 - b. No

BASELINE FORM – CHECK TO BE SURE THAT Consent section is “yes”.

SECTION 1 – Baseline Questions To be asked and entered by research coordinator/assistant, not blinded.

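### Provider adoption is computed from the clinical-exclusion sign-off with no defined denominator, so depending on the reading it penalises correct exclusions or is 100% by construction

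*Combined protocol and SAP*

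**What the plan says.** The measure appears three times. Section 9.5, under feasibility of recruitment and retention, says: "Provider adoption will be assessed by the proportion of their eligible patients that clinicians approve for study participation". Table 1 in section 9.6 gives the ratio as # "approved / # recruited". The text under Aim 2b1 in section 9.6 uses the share of a physician's "recruited patients who are approved for study participation". The same paragraph states the construct: "Provider adoption is defined as the intention to engage with the innovation/intervention".

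Approval itself is described in section 4.3: "If the ED provider determines that patient does not have a clinical condition prohibiting study participation, s/he will sign a study approval form". The form in section 6.2.1 asks the clinician: "please verify you have examined the patient and believe to the best of your knowledge, at this time, that the patient does not have" any of five named conditions (critical status or trauma, bone fracture, joint dislocation, migraine, psychological or psychiatric concern). A sixth line is for clinical judgement or another reason.

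The Appendix B screening form holds two eligibility statuses. Section 2 records the coordinator's, and Section 3 records the clinician's. If a signed form marks the patient not eligible, Section 3 asks "If not eligible, what reason was indicated", answered in free text. A form that was not signed, or not received, ends the process with no reason requested.

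**The concern.** A non-approval can mean two different things. The clinician may have found a condition that the form asks about, which is protocol compliance. Or the clinician may not want the patient in the study, for instance because the same form asks for pain and anxiety medication to be held back in the acupuncture arm. Only the second bears on intention to engage, and no section separates the two when adoption is scored.

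Adoption is one of the named implementation outcomes. It is to be compared across sites and by provider age, race and sex, and the cross-site qualitative analysis then looks for causes of differences in implementation outcomes. A difference produced by what the examination finds could be explained as provider attitude and carried into planning of the definitive trial. A score that cannot move from 100% would hide reluctance altogether.

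**Working it through.** The plan states no target or expected value for adoption, so there is no figure to reproduce.

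**Inputs**
- Order of events (sections 4.3 and 6.2.1): coordinator pre-screen, clinician examination and sign-off, approach, consent.
- Enrollment means consented and randomized (section 6.2.2). Target 150 (section 9.2).
- Consent share: 46/59 = 0.780 in the pilot (section 2.2), and a conservative 50% (section 9.5). I assume these apply to approved patients.
- x = share of screen-eligible patients excluded on examination for a listed condition. Not in the documents; assumed 5% to 10%.
- r = share of the remaining patients whom the clinician declines for other reasons. Not in the documents; assumed 0% or 5%.

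**Reading A: eligible on the coordinator's screen.** Score = (1 - x)(1 - r), while true adoption is 1 - r.
- r = 0: x = 5% gives 0.95; x = 10% gives 0.90. The truth is 1.00.
- r = 5%: 0.95 × 0.95 = 0.9025; 0.90 × 0.95 = 0.855. The truth is 0.95.
- Ranking can reverse. A clinician with x = 10%, r = 0 scores 0.90. One with x = 0, r = 5% scores 0.95, although only the second declined anyone.
- Pooled size with r = 0: approved = 150/0.780 ≈ 192. At x = 5% the screen-eligible number is 192/0.95, about 203 after rounding, so the rate is 192/203 = 94.6% (exact 95% CI 90.5% to 97.3%). At x = 10% it is 192/214 = 89.7% (84.8% to 93.4%). Both intervals exclude the true 100%, so this is bias and not sampling noise.

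**Reading B: confirmed eligible by the clinician.** Every such patient is approved by definition. Score = 100% whatever r is.

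**Reading C: recruited, as in section 9.6.** Approval comes before approach and consent, so every recruited patient has been approved and the Aim 2b1 share is 100%. Table 1, taken literally as a ratio of counts with recruited meaning enrolled, gives 192/150 = 1.28 at 78% consent and (150/0.50)/150 = 300/150 = 2.00 at 50%, which is not a proportion. If recruited loosely means patients put to the clinician, this becomes Reading A.

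**Reading D: meeting sections 4.1 and 4.2 in fact.** Split x into x1 (conditions that section 4.2 excludes) and x2 (conditions on the form that section 4.2 does not exclude as worded). With r = 0 the score is (1 - x1 - x2)/(1 - x1). x2 need not be zero: critical status or trauma is not among the section 4.2 criteria, and fracture, dislocation, migraine and psychiatric concern are excluded there only as the presenting chief complaint. If an assumed x of 10% splits evenly, a fully willing clinician scores 0.90/0.95 = 94.7%.

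**The case against.** The strongest reply is that section 9.5 says eligible. A patient with an excluding condition is not eligible, so a correct exclusion never reaches the denominator. On that view (Reading D) the score can fall below 100% for the right reasons. This has force. A reader might infer that any clinician who excludes a fracture or migraine is certain to be scored as not adopting, and the documents do not support that: it follows only under some readings. But Reading D removes only part of the problem, because the form's list is wider than section 4.2. The form also presents sign-off as a condition of being eligible, which points to Reading B. The term needs a definition.

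A reader might also infer that the adoption rate would mainly reflect case mix. That is not supported. The coordinator already screens for fracture, migraine, dislocation and psychiatric complaints, so only cases found later reach the clinician, and nothing in the documents gives their frequency. At x = r = 5% exclusion and refusal contribute equally. Exclusion shares well above 10% would be speculation.

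The order of sections on the screening form proves little, since Appendix B lets its questions be answered in any order. The sequence rests on sections 4.3 and 6.2.1 instead.

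Finally, much is recoverable. A reason field exists for signed forms, section 4.3 keeps a log of ineligibility reasons, and the study staff interview guide covers physician receptiveness. Adoption has no threshold, test or progression rule. All of that stands and limits the damage, but no section says these data will be used to separate the two kinds of non-approval.

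**Conclusion.** The measure does not isolate the construct that section 9.6 defines. It is taken from a clinical-exclusion check, its denominator is undefined in section 9.5 and different in section 9.6, and no rule says how a non-approval is classified. Under the coordinator-screened reading a fully willing clinician scores 1 - x: 95% to 90% for x of 5% to 10%, lower if x is higher. Under the clinician-confirmed reading, or with recruited patients as denominator, the score is 100% and carries no information. Counting only patients who meet sections 4.1 and 4.2 lies between these and still leaves some correct exclusions as non-adoption.

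The size depends wholly on x, which is an assumption. Making the denominator the same in both sections would not be enough: if both said screen-eligible, correct exclusions would still count against the clinician. This is a validity defect in a descriptive secondary outcome. It is worth correcting because the correction is nearly free.

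**What to change.** Use one definition in section 9.5, in Table 1 and under Aim 2b1 of section 9.6:
- Denominator: screen-eligible patients put to the clinician, minus those excluded for one of the five conditions named on the sign-off form, whether or not the form was signed.
- Numerator: patients approved.
- Report listed-condition exclusions separately, by reason.
- Count exclusions under *Clinical judgement / Other* as non-approval, and show any clinical reason given.
- Report forms not signed or not returned, with no reason known, as their own category. Show adoption with and without them, because non-return may reflect workload.

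In REDCap Section 3, record a reason for every non-approval, signed or not, with the form's listed conditions as coded categories. This matters because section 4.3 describes the clinician signing when no prohibiting condition is found, while Section 3 asks for a reason only when a form was signed. Without the change, a correct exclusion left unsigned would be counted as reluctance again.

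The cost is SAP wording in three places, one REDCap field, and coding of free text already collected. Reasons for forms already left unsigned may not be recoverable. Some *Clinical judgement / Other* entries will be genuine medical reasons, so adoption may be somewhat understated. No clinical rule changes.

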9.5.1 Primary Outcome

The primary objective of the current protocol is to conduct a feasibility RCT to examine the feasibility of refined data collection procedures, and examine intervention implementation and treatment outcomes across sites. As well as, evaluate the feasibility of research procedures, including data quality completeness, participant recruitment and retention, and using study records.

Data Completeness

Using study records and administrative data, we will track recruitment (proportion of eligible patients recruited), document recruitment rates (time to recruit intended sample), and rates of loss to follow up. Data collection forms collected at each time point will be evaluated for quality and completeness. In addition, all quantitative data analyses will be preceded by extensive data checking and verification to identify and resolve the reasons for missing values, inconsistencies, and out-of-range values. Although we anticipate some missing data based on our experience, we will carefully examine whether missingness is completely at random (MCAR), at random (MAR) or informative (MNAR). Models proposed for analysis can handle incomplete data but do require at least that missingness be at random. Modelling will consider using multiple imputation techniques of covariates to reduce potential biases.

Recruitment/Retention

To assess recruitment, we will track the number of eligible patients presenting to the ED during the time of enrolling sessions and the proportion who agree to participate. Basic demographics and presenting complaint will be collected for all eligible patients, allowing us to identify subgroups who are more or less likely to participate. Similarly approaches will be used to assess rates of loss to follow up at all data collection points. We will assess variables across different patient groups (including age, race, sex), and across the study arms as well as overall and by sites.

